More specifically, continuous dosing of mirdametinib was utilized at doses ranging from 10 mg BID to 20 mg BID in advanced cancer but transitioned to alternative intermittent schedules following the occurrence of 2 events of retinal vein occlusion (RVO) at 10 mg BID and 15 mg BID on the continuous schedule. Subsequent analysis of relevant visual adverse events found predisposing risk factors for retinopathy in both subjects experiencing an RVO. Notably, as mentioned previously, the next dose and schedule evaluated was both significantly dose reduced (2 mg/m² BID; maximum dose 4 mg BID) and given on an intermittent schedule (3 weeks on, 1 week off). As a result, an evaluation of mirdametinib at doses between 2 mg/m² – 10 mg/m² on a continuous basis has not been performed leaving a wide gap in the safety and tolerability information of this agent. Further, on the aforementioned study above (4 mg BID dosing) showed general good tolerability (see section 3) with no RVOs reported.

Memorial Sloan Kettering Cancer Center
[name]
[name]

Last, we also note the low likelihood of interaction between fulvestrant and mirdametinib as their toxicity profiles are orthogonal, and fulvestrant is generally extremely well tolerated.

Due to the knowledge gained in this retrospective review, the implementation of screening for RVO risk factors prior to the initiation of mirdametinib therapy and the class experience of other MEK inhibitors administered on a continuous schedule, we propose the evaluation of mirdametinib beginning at 4 mg BID, on a continuous schedule in a controlled clinical trial setting. To ensure that the dose selected is feasible, tolerable, and beneficial, we are planning a phase 1 dose escalation in standard 3+3 design. However, to be conservative with this clinical trial design, in addition to dose de-escalation, we additionally have added intermittent dose dosing levels on mirdametinib de-escalation, in the case that continuous dosing is poorly tolerated.

The starting dose of mirdametinib in combination with fulvestrant in each Dose Level will be as follows:

- Dose Level 1: mirdametinib 4 mg BID PO + fulvestrant
- (Only to be triggered pending DLTs on higher Dose Levels as described below)
 - Dose Level -2: mirdametinib 2 mg BID PO continuous + fulvestrant, and Dose Level -2INT: mirdametinib 2 mg BID PO on 3 weeks on, 1 week off + fulvestrant

The 3+3 decisions in Part 1 of Arm 1 will be made as follows.

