1. Mirdametinib starting dose Dose Level 1 (4 mg BID PO given continuously)
 - a. Up to 3 subjects will be treated with mirdametinib 4 mg BID PO given continuously in combination with the recommended dose of fulvestrant.
 - b. If ≤ 1 of the first 3 evaluable subjects in Dose Level 1 exhibit a DLT in Cycle 1, then Dose Level 1 will be expanded (see #2 below).
 - c. Mirdametinib dose in combination with fulvestrant will not be escalated above the 4 mg BID dose level.
2. Dose Level 1 expansion:
 - a. A sufficient number of subjects will be treated with mirdametinib 4 mg BID PO given continuously in combination with the recommended dose of fulvestrant to accrue 6 evaluable subjects.
 - b. If ≤ 1 of 6 evaluable subjects in the starting Dose Level exhibit a DLT in Cycle 1, then **mirdametinib 4 mg BID PO** given continuously will be declared as the recommended dose for Part 2 (RP2D) in combination with fulvestrant.
 - c. If ≥ 2 of the first 3 evaluable subjects or ≥ 2 of the 6 evaluable subjects in Dose Level 1 exhibit a DLT in Cycle 1, then the mirdametinib dose will be de-escalated (see #3 below, Dose Level -2).

Memorial Sloan Kettering Cancer Center
[name]
[name]

3. Mirdametinib Dose Level -2 (de-escalation Dose Level at 2 mg BID PO given continuously)
 - a. Up to 3 subjects will be treated with mirdametinib 2 mg BID PO given continuously in combination with the recommended dose of fulvestrant in Dose Level -2
 - b. If 1 of the first 3 evaluable subjects in Dose Level -2 exhibit a DLT in Cycle 1, then a sufficient number of subjects will be treated with mirdametinib 2 mg BID PO given continuously in combination with the recommended dose of fulvestrant to accrue 6 evaluable subjects.
 - c. If ≤ 1 of 6 evaluable subjects in Dose Level -2 exhibit a DLT in Cycle 1, then **mirdametinib 2 mg BID PO** given continuously will be declared as the recommended dose for Part 2 (RP2D) in combination with fulvestrant.
 - d. If ≥ 2 of the first 3 evaluable subjects or ≥ 2 of the 6 evaluable subjects in Dose Level -2 exhibit a DLT in Cycle 1, then the Arm 1 will be further de-escalated (see #4 below).
4. Mirdametinib Dose Level -2INT (de-escalation Dose Level at 2 mg BID PO on a 3 weeks on, 1 week off schedule)
 - a. Up to 3 subjects will be treated with mirdametinib 2 mg BID PO given intermittently in combination with the recommended dose of fulvestrant in Dose Level -2INT

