At each step of the 3+3 design, the investigators will review all available safety and PK data in the current Dose Level and decide about the appropriate next step. The subjects will become evaluable for the 3+3 decisions if they complete Cycle 1 and receive at least 80% of assigned drug doses, or if they exhibit a DLT in Cycle 1.

The starting dose of mirdametinib as single agent in each Dose Level escalation will be as follows:

- Dose Level 1: **mirdametinib 4 mg BID PO**, given continuously
- Dose Level 2: **mirdametinib 6 mg BID PO**, given continuously
- Dose Level 3: **mirdametinib 8 mg BID PO**, given continuously
- The de-escalation (Dose Level -1) may evaluate **mirdametinib 3 mg BID** given continuously, and (Dose Level -1INT) may evaluate **mirdametinib 3 mg BID** given on a 3 weeks on, 1 week off schedule. These de-escalation Dose Levels will be evaluated at investigator's discretion after the higher dose of mirdametinib is not tolerated. The de-escalation Dose Levels will be started only if the benefit-risk ratio is acceptable at the investigator's opinion.

The 3+3 decisions in Part 1 of Arm 2 will be made as follows.

1. Dose Level 1 (**mirdametinib 4 mg BID PO** given continuously)
 - a. Up to 3 subjects will be treated with mirdametinib as single agent at the dose of **4 mg BID PO** given continuously.

Memorial Sloan Kettering Cancer Center
[name]
[name]

- b. If 1 of the first 3 evaluable subjects in Dose Level 1 exhibit a DLT in Cycle 1, then Dose Level 1 will be expanded (see #2 below)
- c. If 0 of the first 3 evaluable subjects in Dose Level 1 exhibit a DLT in Cycle 1, then the dose of mirdametinib as single agent will be escalated to Dose Level 2 (**6 mg BID** given continuously) (see #4 below)

2. Dose Level 1 expansion:

- a. A sufficient number of subjects will be treated with mirdametinib as single agent at the dose of **4 mg BID PO** given continuously to accrue 6 evaluable subjects.
- b. If ≤ 1 of 6 evaluable subjects in the starting Dose Level exhibit a DLT in Cycle 1, then the dose of mirdametinib as single agent will be escalated to Dose Level 2 (**6 mg BID** given continuously) (see #5 below).
- c. If ≥ 2 of the first 3 evaluable subjects or ≥ 2 of the 6 evaluable subjects in Dose Level 1 exhibit a DLT in Cycle 1, then the mirdametinib dose will be de-escalated (see #3 below).

3. Dose Level -1 (de-escalation Dose Level **3 mg BID PO** given continuously)

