- a. Up to 3 subjects will be treated with mirdametinib as a single agent at the dose of 3 mg BID PO in Dose Level -1
- b. If ≤ 1 of the first 3 evaluable subjects in Dose Level -1 exhibit a DLT in Cycle 1, then a sufficient number of subjects will be treated with **mirdametinib 3 mg BID PO** given continuously to accrue 6 evaluable subjects.
- c. If ≤ 1 of 6 evaluable subjects in Dose Level -1 exhibit a DLT in Cycle 1, then **mirdametinib 3 mg BID PO** given continuously will be declared as the recommended dose for Part 2 (RP2D).
- d. If ≥ 2 of the first 3 evaluable subjects or ≥ 2 of the 6 evaluable subjects in the de-escalation Dose Level exhibit a DLT in Cycle 1, then the Arm 2 will be further de-escalated (see #4 below).

4. Dose Level -1INT (de-escalation Dose Level **3 mg BID PO** on a 3 weeks on, 1 week off schedule)

- a. Up to 3 subjects will be treated with mirdametinib as a single agent at the dose of 3 mg BID PO intermittently in Dose Level -1INT
- b. If ≤ 1 of the first 3 evaluable subjects in Dose Level -1INT exhibit a DLT in Cycle 1, then a sufficient number of subjects will be treated with **mirdametinib 3 mg BID PO** intermittently to accrue 6 evaluable subjects.
- c. If ≤ 1 of 6 evaluable subjects in Dose Level -1INT exhibit a DLT in Cycle 1, then **mirdametinib 3 mg BID PO** intermittently will be declared as the recommended dose for Part 2 (RP2D).

- d. If ≥ 2 of the first 3 evaluable subjects or ≥ 2 of the 6 evaluable subjects in the de-escalation Dose Level exhibit a DLT in Cycle 1, then the Arm 2 will be discontinued. The reason for discontinuation of Arm 2 would be that **3 mg BID PO** intermittently is deemed to be the minimum dose required for sufficient clinical benefit from mirdametinib as single agent in the refractory advanced cancer.

5. Dose Level 2 (Dose Level escalation **6 mg BID PO** given continuously)

- a. Up to 3 subjects will be treated with mirdametinib as a single agent at the dose of **6 mg BID PO** given continuously in Dose Level 2
- b. If ≤ 1 of the first 3 evaluable subjects in Dose Level 2 exhibit a DLT in Cycle 1, then a sufficient number of subjects will be treated with mirdametinib **6 mg BID PO** given continuously to accrue 6 evaluable subjects.
- c. If ≤ 1 of 6 evaluable subjects in Dose Level 2 exhibit a DLT in Cycle 1, then the dose of mirdametinib as single agent will be escalated to Dose Level 3 (**8 mg BID** given continuously) (see #6 below).

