- d. If ≥ 2 of the first 3 evaluable subjects or ≥ 2 of the 6 evaluable subjects in Dose Level 2 exhibit a DLT in Cycle 1, then **mirdametinib 4 mg BID PO** given continuously will be declared as the recommended dose for Part 2 (RP2D).

6. Dose Level 3 (Dose Level escalation **8 mg BID PO** given continuously)

- a. Up to 3 subjects will be treated with mirdametinib as a single agent at the dose of **8 mg BID PO** in Dose Level 3
- b. If ≤ 1 of the first 3 evaluable subjects in Dose Level 3 exhibit a DLT in Cycle 1, then a sufficient number of subjects will be treated with mirdametinib **8 mg BID PO** given continuously to accrue 6 evaluable subjects.
- c. If ≤ 1 of 6 evaluable subjects in Dose Level 3 exhibit a DLT in Cycle 1, then **mirdametinib 8 mg BID PO** given continuously will be declared as the recommended dose for Part 2 (RP2D).
- d. If ≥ 2 of the first 3 evaluable subjects or ≥ 2 of the 6 evaluable subjects in Dose Level 3 exhibit a DLT in Cycle 1, then **mirdametinib 6 mg BID PO** given continuously will be declared as the recommended dose for Part 2 (RP2D).
- e. The dose of mirdametinib as single agent will not be escalated above **8 mg BID PO** given continuously.

Arm 2 – Part 2 (expansion cohorts for mirdametinib as single agent)

One or more expansion cohorts (up to 30 subjects each) will be started, either in parallel or sequentially depending on the results of Part 1. The purpose will be to evaluate the efficacy and safety of the RP2D of mirdametinib as single agent (as determined in Part 1 of Arm 2) in the subjects with advanced solid cancers (with the exception of colorectal, small bowel, biliary and ampullary cancers) harboring activating mutations in MEK1/2.

Memorial Sloan Kettering Cancer Center
[name]
[name]

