14.0 BIOSTATISTICS

14.1 Analysis Populations

The following analysis populations will be used:

- **DLT Evaluable Population** consists of patients who receive at least 80% of planned total doses of mirdametinib in cycle 1 (in Arm 1 only, also both doses of fulvestrant) and are observed within 28 days following the first dose of mirdametinib or patients who experience a DLT.
- **Efficacy Population**, used for the assessment of efficacy for each arm, will consist of all patients in Part 2 who received at least 1 dose of study drug and who have at least 1 post-baseline tumor assessment. Arms 1 and 2 will be analyzed separately. In addition, patients treated at the MTD in the dose escalation portion of the protocol (both arms 1 and 2) will be included in the efficacy analyses for the expansion cohorts in part 2 if they meet the requirements for efficacy population as defined above. Additionally, the RP2D will be determined pending the clinical data obtained in the dose escalation portion of the protocol. If the RP2D is less than the MTD, then patients treated at the RP2D in the dose escalation portion of the protocol (both arms 1 and 2) will be included in the

Memorial Sloan Kettering Cancer Center
[name]
[name]

efficacy analyses for the expansion cohorts in part 2 if they meet the requirements for efficacy population as defined above.

- **Pharmacokinetic Population**, used for the assessment of pharmacokinetic endpoints, will consist of all patients who have sufficient pharmacokinetic concentration data recorded to derive pharmacokinetic endpoints.
- **All treated population or safety population:** consisting of all patients who receive any amount of drug

Arms 1 and 2 will be analyzed separately throughout the study.

Arm 1

The study will follow a standard 3+3 dose escalation schema. As described previously in section 4.2, the 3+3 decisions in Part 1 of Arm 1 will be made starting with a mirdametinib starting dose level (4 mg BID PO), where subjects will be treated with mirdametinib 4 mg BID PO given continuously in combination with the recommended dose of fulvestrant. If ≤ 1 of the first 3 DLT evaluable subjects in Dose Level 1 exhibit a DLT in Cycle 1, then Dose Level 1 will be expanded. Mirdametinib dose in combination with fulvestrant will not be escalated above the 4 mg BID given continuously dose level.

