fulvestrant. If 1 of the first 3 evaluable subjects in Dose Level -2INT exhibit a DLT in Cycle 1, then a sufficient number of subjects will be treated with mirdametinib 2 mg BID PO on a 3 weeks on, 1 week off schedule, in combination with the recommended dose of fulvestrant to accrue 6 evaluable subjects. If 1 of 6 evaluable subjects in Dose Level -2INT exhibit a DLT in Cycle 1, then **mirdametinib 2 mg BID PO on a 3 weeks on, 1 week off schedule**, will be declared as the recommended dose for Part 2 (RP2D) in combination with fulvestrant. If ≥ 2 of the first 3 evaluable subjects or ≥ 2 of the 6 evaluable subjects in Dose Level -2INT exhibit a DLT in Cycle 1, then Arm 1 will be discontinued. In the case of de-escalation there will be at least 18 evaluable patients (6 from dose level 0, and 6 on two separate dose levels of de-escalation).

Arm 2

Part 1 will be conducted in three sequential Dose Level escalations according to the 3+3 design based on the incidence of dose-limiting toxicities (DLT) and the overall safety profile of the study treatments. At each step of the 3+3 design, the investigators will review all available safety and PK data in the current Dose Level and decide about the appropriate next step. The subjects will become evaluable for the 3+3 decisions if they complete Cycle 1 and receive at least 80% of assigned drug doses, or if they exhibit a DLT in Cycle 1. The starting dose of mirdametinib as single agent in each dose escalation dose level will be as follows: mirdametinib 4 mg BID PO given continuously, mirdametinib 6 mg BID PO given continuously, mirdametinib 8 mg BID PO given continuously. The de-escalation Dose Levels (Dose Level -1) may evaluate mirdametinib 3 mg BID given continuously and (Dose Level -1INT) may evaluate mirdametinib 3 mg BID given on. 3 weeks on, 1 week off schedule.

The 3+3 decisions in Part 1 of Arm 2 will be made similar to the above. Up to 3 subjects will be treated with mirdametinib as single agent at the dose of **4 mg BID PO** given continuously. If ≤ 1 of the first 3 evaluable subjects in Dose Level 1 exhibit a DLT in Cycle 1, then Dose Level 1 will be expanded. If 0 of the first 3 evaluable subjects in Dose Level 1 exhibit a DLT in Cycle 1, then the dose of mirdametinib as single agent will be escalated to Dose Levels 2 and 3 (**6 mg BID** given continuously **and 8 mg BID** given continuously) following the same rules as above. There will thus be as many as 18 evaluable patients on this arm.

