The following table shows the corresponding probability of escalating given five hypothetical true risk for DLT.

True risk of DLT	0.1	0.2	0.3	0.4	0.5
Probability of escalation	0.9	0.7	0.5	0.3	0.2

Memorial Sloan Kettering Cancer Center
[name]
[name]

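### Arm 2 can declare 4 mg BID the RP2D on three patients (0/3 DLTs), while every other RP2D declaration in section 4.2 rests on at most 1 DLT in 6

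*Combined protocol and SAP*

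**What the plan says.** **Arm 2 Part 1 (section 4.2).** Step 1b expands 4 mg BID to six evaluable patients only when exactly one of the first three has a DLT. Step 1c covers the clean result: "If 0 of the first 3 evaluable subjects in Dose Level 1 exhibit a DLT in Cycle 1, then the dose of mirdametinib" goes up to 6 mg BID. Step 5d covers failure at 6 mg: if at least two of the first 3, or of 6, "in Dose Level 2 exhibit a DLT in Cycle 1, then mirdametinib 4 mg BID PO given continuously will be declared as the" RP2D. It sets no condition on how many patients were treated at 4 mg.

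**The other declarations in 4.2.**
- Arm 1, step 2b, same 4 mg continuous dose: "If ≤ 1 of 6 evaluable subjects in the starting Dose Level exhibit a DLT in Cycle 1, then mirdametinib 4 mg BID PO" becomes the RP2D. Steps 1b and 2a fill that level to six even after 0/3.
- Arm 1, steps 3c and 4c (2 mg continuous, 2 mg intermittent): at most 1/6.
- Arm 2, step 3c: "If ≤ 1 of 6 evaluable subjects in Dose Level -1 exhibit a DLT in Cycle 1, then" 3 mg is declared. Steps 4c (3 mg intermittent) and 6c (8 mg) use the same rule.
- Arm 2, step 6d (6 mg): also at most 1/6, because 5b fills 6 mg to six even after 0/3 and 5c requires at most 1/6 before 8 mg.

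**Section 14.1, Arm 2.** One sentence expands Dose Level 1 on at most one DLT in three, and the next escalates on none: "then Dose Level 1 will be expanded. If 0 of the first 3 evaluable subjects in Dose Level 1 exhibit a DLT in" Cycle 1, the dose goes up. The table that follows is introduced with "The following table shows the corresponding probability of escalating given five hypothetical true risk for DLT".

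**The concern.** The plan sets its own standard for calling a dose the RP2D, at most 1 DLT in 6 evaluable patients, and one branch omits it. On that branch 4 mg is accepted on three patients just after the next level, 2 mg BID higher, has failed.

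Safety and tolerability are the primary objective, and the declared dose goes into up to two Arm 2 expansion cohorts of up to 30 patients each. After Part 1 there is no cohort-level numeric toxicity rule, only the general termination grounds in section 12.0 and the DSMC oversight in 16.4. On dosing between 2 and 10 mg/m², section 4.2 (dose selection) says an evaluation "on a continuous basis has not been performed leaving a wide gap in the safety and tolerability information of this agent". Those are the conditions in which the six-patient standard is useful.

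**Working it through.** **1. Which reading of 0/3 does the plan use?** Section 14.1 gives 0/3 two instructions, so I compared both with the printed escalation table. For true DLT risk p:

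- Escalate on 0/3 or 1/6: (1−p)³ + 3p(1−p)² × (1−p)³
- Fill to six first: P(at most 1 DLT in 6)

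| p | 0.1 | 0.2 | 0.3 | 0.4 | 0.5 |
|---|---|---|---|---|---|
| Printed in 14.1 | 0.9 | 0.7 | 0.5 | 0.3 | 0.2 |
| Escalate on 0/3 or 1/6 | 0.906 | 0.709 | 0.494 | 0.309 | 0.172 |
| Fill to six first | 0.886 | 0.655 | 0.420 | 0.233 | 0.109 |

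The first rule rounds to every printed value; the second misses at 0.3, 0.4 and 0.5. Enumerating all Arm 2 paths in 4.2, with de-escalation always pursued, gives 6 to 18 DLT-evaluable patients, as stated in 14.5. The only six-patient path is 0/3 at 4 mg, at least 2/3 at 6 mg, then 4 mg declared. The plan's own figures therefore assume the three-patient route.

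**2. What each result says about the DLT rate.** Two-sided 95% Clopper-Pearson upper limits:
- 0/3: 71% (0.708)
- 1/6, the weakest result that meets the plan's standard: 64% (0.641)
- 0/6: 46% (0.459)

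**3. Share of 4 mg declarations that rest on three patients.** Both routes to a 4 mg RP2D need 6 mg to fail, so that factor cancels. The share is (1−p)³ / [(1−p)³ + 3p(1−p)²(1−p)³] = 1 / [1 + 3p(1−p)²]. For p = 0.1 to 0.5 this gives 0.805, 0.723, 0.694, 0.698 and 0.727, or 69–80%.

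**4. How often the route occurs, and how often filling to six changes the answer.** The protocol gives no DLT rates by dose, so these are assumptions. The first column is the assumed true rate at 4 mg / 6 mg.
- Route = (1−p₄)³ × P(at least 2 of 6 at p₆)
- Reversal given the route = P(at least 2 of the next 3 at p₄) = 3p₄²(1−p₄) + p₄³

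| 4 mg / 6 mg | Route | Reversal given route | Reversal, all trials |
|---|---|---|---|
| 0.10 / 0.10 | 0.729 × 0.114 = 0.083 | 0.028 | 0.2% |
| 0.10 / 0.20 | 0.729 × 0.345 = 0.251 | 0.028 | 0.7% |
| 0.20 / 0.40 | 0.512 × 0.767 = 0.393 | 0.104 | 4.1% |
| 0.30 / 0.50 | 0.343 × 0.891 = 0.305 | 0.216 | 6.6% |

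**5. Effect of the fix on Part 1 size.** I enumerated every path, assuming DLT rates of 0.10 (3 mg intermittent), 0.15 (3 mg), 0.20 (4 mg), 0.40 (6 mg) and 0.50 (8 mg). The current rules give a range of 6–18 and a mean of 10.5. With 4 mg completed to six before declaration, the range is 9–24 and the mean 12.0, and the size exceeds 18 in 0.8% of trials.

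**The case against.** The strongest reply is that little turns on this.

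- **Small effect.** Reversal is at most 6.6% in the scenarios above, and that needs a true 4 mg rate of 0.30. At 0.10 it is below 1%.
- **Thin contrast in evidence.** The 95% limits for 0/3 and 1/6 are 71% and 64%. At a one-sided 80% level they are 41.5% and 42.2%, so 0/3 is not clearly worse than a 1/6 the plan accepts.
- **A deliberate choice.** Section 14.5 anticipates as few as six patients in Arm 2, which happens only on this route.
- **Other protection.** Tables 4 and 5 give patient-level interruption, reduction and stopping rules. Eye and cardiac checks recur every odd cycle, and safety and PK data are reviewed at each step. Section 3.2 describes 4 mg BID as generally well tolerated on the intermittent schedule and places DLTs on continuous dosing at 10 mg BID and above. Arm 1 tests the same dose with fulvestrant.
- **Limits of the comparison.** The 14.1 table does not fit the 6 mg to 8 mg step, where 5b fills to six even after 0/3. In Arm 1, steps 3b and 4b give no instruction for 0/3.

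The first two points stand and keep the matter moderate. The third shows that the route was counted, but the plan does not explain why this declaration alone needs three patients. The patient-level rules and reviews set no six-patient minimum for Arm 2, and 14.1 analyses the arms separately. The table's misfit at a higher step does not alter its fit at Dose Level 1. The undefined 0/3 step in Arm 1 still leads to declarations that require at most 1/6.

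**Conclusion.** The concern holds. Steps 1c and 5d together let 4 mg BID be declared the Arm 2 RP2D on 0/3, and this is the only declaration in 4.2 that does not rest on at most 1/6 at the declared dose. Section 14.1 does not close the gap, because its wording for 0/3 conflicts and its table fits the three-patient reading.

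The route is the usual way to a 4 mg RP2D and occurs in 8% to 39% of trials across the assumed scenarios. Once it is taken, three more patients would overturn the declaration with probability 3%, 10% or 22% at a true 4 mg rate of 0.1, 0.2 or 0.3. The route and reversal figures depend on those assumed rates; the 69–80% share does not depend on the 6 mg rate. The change should be made because it is cheap and restores the plan's own standard, although the effect on decisions is only moderate.

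**What to change.** 1. **Section 4.2, Arm 2, step 5d.** Add that if Dose Level 1 has only three evaluable subjects, it is completed to six in Part 1 before 4 mg BID is declared. Declaration then requires at most 1/6; otherwise step 2c (de-escalation) applies.
2. **Section 14.1, Arm 2.** Change the Dose Level 1 expansion trigger from at most 1 to exactly 1 of the first 3, to agree with steps 1b and 1c and with the table.
3. **Section 4.2, Arm 2, step 1c.** Correct the pointer from #4 (3 mg intermittent) to #5 (6 mg).
4. **Sections 14.1 and 14.5.** Restate the Part 1 size. The smallest path ending in a 4 mg RP2D becomes 9 (3 + 3 + 3), and the maximum becomes 24 (6 each at 4 mg, 6 mg, 3 mg and 3 mg intermittent).

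**Cost.** On this route only: three more Part 1 patients, about 1.5 months of accrual (3 patients at two per month) plus one 28-day cycle. These patients need not be lost to Part 2. Under 14.1, "patients treated at the MTD in the dose escalation portion of the protocol (both arms 1 and 2) will be included in the" expansion-cohort efficacy analyses, and the same applies to patients treated at an RP2D below the MTD, provided they have a post-baseline tumor assessment.

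Filling 4 mg to six before escalating would keep the maximum at 18, but it would add patients on every path that starts with 0/3.
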